### 6.3.2 Depression

The sample size, mean, median, SD, minimum, and maximum values for the PHQ-9 will be presented for the baseline visit.

### 6.3.3 PTSD

The sample size, mean, median, SD, minimum, and maximum values for the PCL-5 will be presented for the baseline visit using the total summary score.

#### 6.3.4 VR-12

The sample size, mean, median, SD, minimum, and maximum values for the PCS and MCS scores from the VR-12 will be presented for the baseline visit.

#### 6.3.5 PSQI

The sample size, mean, median, SD and minimum and maximum values for the 7 component scores including sleep duration, sleep disturbance, sleep latency, day dysfunction due to sleepiness, sleep efficiency, overall sleep quality and needs medications to sleep will be reported for the baseline visit. In addition, the sample size, mean, median, SD and minimum and maximum values for the overall PSQI total score will be presented for the baseline visit. See Appendix 2 for PSQI scoring algorithms.

#### 6.3.6 C-SSRS

The number and percentages of participants with suicidality will be reported for the baseline visit.

### 6.4 Treatment Exposure

The number and percentages of randomized subjects in each treatment group by Month.

- Months of treatment will be calculated using date of pairing (day the training begins) for the Service Dog group.
- Months of treatment will be calculated using date dog was received for Emotional Support Dog group.

## 7 STATISTICAL ANALYSES

### 7.1 Primary Outcomes

The primary objective of this study is to determine how the provision of a Service Dog or an Emotional Support Dog impacts activity and quality of life for Veterans with PTSD. Primarily, the objective is to compare activity limitations and quality of life change, relative to baseline, over the 18-month intervention period between the two groups of Veterans with PTSD, i.e., those who receive Service Dogs and those who receive Emotional Support Dogs. There are two primary outcomes in this study: 1) improvement in activity as assessed by the total WHO-DAS 2.0 score and 2) improvement in quality of life as assessed by the Physical Component Scale (PCS) and Mental Component Scale (MCS) of the VR-12. The outcome measure for the first primary objective will be the change in the WHO-DAS 2.0 score over the 18 months of the intervention phase adjusted by baseline scores. The outcome measures for the other primary objectives will be the relative change in the PCS and MCS scores over the 18 months of the intervention phase adjusted by the baseline scores. The WHO-DAS 2.0 and VR-12 will be assessed at baseline, clearing and at 3, 6, 9, 12, 15 and 18-month post-pairing visits.

To begin the analyses, the distribution of each variable will be examined for outliers and to determine if transformations (to normalize data) are necessary. The mean and standard deviation of the activity level (WHO-DAS 2.0 summary score) and quality of life (PCS and MCS score) will be calculated at each time point during the screening/clearing and then during the follow-up phase (TABLES 9 & 10). During the follow-up phase, the activity level will be calculated separately for those veterans paired who were assigned to the Service Dog group as well as the Emotional Support Dog group.

The following are hypothesized for this study:

- For the WHO-DAS 2.0 outcome: Veterans who receive Service Dogs will have decreased activity limitations over time, as compared to Veterans who receive Emotional Support Dogs.
- For the VR-12 outcomes, Veterans who receive Service Dogs will have improved quality of life over time, as compared to Veterans who receive Emotional Support Dogs.

For the first hypothesis, a generalized linear mixed model (GLMM) will be used to determine changes over time between groups. Thus the level-1 units consist of the repeated measures, WHODAS 2.0 score, for each subject, and the level-2 unit is the individual or subject. In addition to estimating overall parameter estimates, multilevel modeling for repeated measures allows regression equations at the level of the individual (Curran, 2010). One of the major advantages of multivariate multiple regression is that outcomes with more missing data can "borrow information" from outcomes with less missing data (McCulloch, 2008). The use of mixed models allows for control of covariance data expected in clustered and repeatedly sampled data, and missing data. The statistical tests for the primary outcome measure will be two-sided at a 5% Type I error rate. Confidence intervals will be two-sided with a 95% confidence level.

The primary analysis will include gender and site in the model. Other variables will be examined, including other demographic factors, to determine if any significant differences exist. If a variable is considered to be a potential confounder, it may be included in the model as a covariate. See TABLE 13 for example reporting tables.

For the second hypotheses, a generalized linear mixed model (GLMM) will be used to determine changes over time on PCS and MCS scores between groups. The level-1 unit will be the repeated measure. In the first model, PCS will be the level-1 unit; in the second model, MCS will be the level-1 unit. The level-2 unit in both models will be the individual or subject. The statistical tests for the primary outcome measure will be two-sided at a 5% Type I error rate. Confidence intervals will be two-sided with a 95% confidence level. As described above, any variable considered to be a potential confounder may be added to the models.

An additional analysis for all hypotheses will use the linear repeated mixed models, with random intercepts. When random coefficients are specified, each subject has its own regression equation, making it possible to evaluate whether subjects differ in their means and/or response patterns over time. The WHODAS 2.0 summary scores will be regressed on time and the group x time interaction with random intercepts added for participants that will account for the correlation among repeated measures.

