In order to detect a 10-point difference in treatment group mean scores for the WHO-DAS 2.0 over the 18 months of follow-up, at a statistical significance level of 0.05 (two-tailed test) and a power of 0.85, 32 participants per group will be needed (see Table 6). In order to detect a 15% difference in mean scores for MCS over the 18-months of follow-up, at a statistical significance level of 0.05 (two tailed test) and a power of 0.85, 82 participants per group will be needed (see Table 6). In order to detect a 15% difference in mean scores for the PCS over the 18-months of follow-up, at a statistical significance level of 0.05 (two tailed test) and a power of 0.85, 60 participants per group will be needed (see Table 6). The sample size estimates were obtained using the PC-software SAS 9.2.

Assuming the largest of the three sample sizes, 82 participants per group, and a maximum of 25% participant loss or dropout rate a sample size of 110 participants per treatment will be required for this study. To obtain the necessary sample size of 220 participants, at least three VA medical centers will be recruited. Once a participant has been determined to be eligible for the study at the participating VA medical center, randomization to one of the two groups will be accomplished by a telephone call to the Perry Point Coordinating Center. All sites will be encouraged to recruit and enroll participants faster than the stated requirements.

- **Statistical Methods**

The intent-to-treat population (ITT) is defined as the population of participants who will be randomized in either the Service Dog (SERV) or Emotional Support Dog (EMOT) treatment groups. The participants will be categorized based on their initial randomized group assignment and will be included in analyses irrespective of their status – completer or drop out of the study before completion. A per protocol population (PP) is defined as the population of participants who are paired with a dog. Analyses of all outcome measures – primary and secondary – will use both the ITT and PP population.

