All statistical tests will be 2-sided and at 5% level of significance. SAS 9.2 or higher will be used to conduct all statistical analyses. Initial analysis of all hypotheses will involve the examination of simple descriptive statistics. Frequencies and proportions will be reported for all categorical variables. Continuous variables will be described with either means and standard deviations or medians and other percentiles depending on whether or not the variables are approximately normally distributed. In some instances, simple descriptive statistics will be the primary statistics of interest. In most cases, these will be preliminary to the analyses described below.

- **Primary Outcome Measures**

Activity Limitations: The WHODAS-2.0 was developed to assess disability related to physical and psychiatric disorders experienced within the past 30 days and provides a profile of functioning across six activity domains: understanding and communicating, mobility, self-care, getting along with others, life activities, and participation in society, as well as an overall summary score. WHO-DAS 2.0 summary scores can range from 0 (no disability) to 100 (full disability). The level of activity will be based upon the WHO-DAS 2.0 Summary Score measured at baseline, clearing, and 3, 6, 9, 12, 15 and 18 months post-pairing. To begin the analyses, the mean and standard deviation of the activity level will be calculated separately, at each time point, for participants assigned to the Service Dog group and the Emotional Support Dog group. We hypothesize that participants who receive Service Dogs will have decreased activity limitations over time, as compared to participants who receive an Emotional Support Dog.

For this hypothesis, a linear repeated measures mixed model will be used to determine changes over time between groups. Thus the level-1 units consist of the repeated measures, WHODAS 2.0 score, for each subject, and the level-2 unit is the individual or subject. In addition to estimating overall parameter estimates, multilevel modeling for repeated measures allows regression equations at the level of the individual (Curran, 2010). WHODAS 2.0 summary scores will be considered as the dependent variable. Other variables found to be potential confounders will also be included in the model as covariates. The use of mixed models allows for control of covariance data expected in clustered and repeatedly sampled data, and missing data.

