## 2 STUDY OBJECTIVES AND ENDPOINTS

### 2.1 Study Objectives and Hypotheses

#### Primary Objectives:

**Objective 1: To examine how limitations on activity and quality of life in Veterans with PTSD are impacted by the provision of a Service Dog versus an Emotional Support Dog.**

Limitation on activity is defined as the inability to fully engage in important life domains, such as cognition, mobility, self-care, and participation in society. For all the hypotheses listed below we will examine change over the 18-month intervention period between the two groups of participants with PTSD: those who are paired with a Service Dog and those who are paired with an Emotional Support Dog.

*Hypothesis 1a: Compared to Veterans who receive an Emotional Support Dog, Veterans who receive Service Dogs will have improved ability to fully engage in important life domains over time as measured by the WHO-DAS 2.0 domain scores and the WHO-DAS 2.0 total score.*

*Hypothesis 1b: Compared to Veterans who receive an Emotional Support Dog, Veterans who receive Service Dogs will have improved quality of life, as measured by the global mental and physical health component scores of the VR-12.*

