## 2.2 Endpoints

### 2.2.1 Primary Outcome Measures

The primary outcome measures include limitations of activity and quality of life.

For hypothesis 1a: The outcome measure will define activity limitations as measured by the World Health Organization Disability Assessment Scale II (WHODAS 2.0). The WHODAS 2.0 is a structured 36 item instrument which assesses difficulties in six domains of life during the last 30 days. The six domain scores and the total WHO-DAS 2.0 score will be utilized for this hypothesis.

For hypothesis 1b: The outcome measure will be the summary measures from the VR-12 instrument of health-related quality of life as measured by the Physical Component Summary (PCS) and Mental Component Summary (MCS).

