#### **5.4 General Considerations**

This section details general policies to be used for the statistical analyses. Departures from these general policies may be given in the specific detailed sections of this statistical analysis plan. When this situation occurs, the rules set forth in the specific section take precedence over the general policies. The following policies will be applied to all data presentations and analyses.

- All p-values will be rounded to 3 decimal places. All p-values that round to 0.000 will be presented as ‘<0.001’ and p-values that round to 1.000 will be presented as ‘>0.999’. Any p-value  $\leq \alpha$  will be considered statistically significant and will be marked with one asterisk (e.g., 0.026\*).
- Summary statistics will consist of the number and percentage of responses in each category for discrete variables, and the mean, median, standard deviation (SD), minimum, and maximum for continuous variables.
- All mean and median values will be formatted to one more decimal place than the measured value. Standard deviation values will be formatted to two more decimal places than the measured value.
- All percentages will be rounded to one decimal place. The number and percentage of responses will be presented in the form XX (XX.X), where the percentage is in the parentheses. The decimal of the percentage may be dropped due to space constraints when creating a table.
- All listings will be sorted for presentation in order of treatment group, site number, subject number, and date of procedure or event.
- When necessary for analysis purposes, partial dates will be completed (i.e., turned into complete dates) using the most conservative approach.
- All analysis and summary tables will have the population sample size for each group or treatment group in the column heading.
- The baseline for the WHO-DAS 2.0, PCL, PSQI, VR-12, C-SSRS and PHQ-9 is the Home Visit (or Baseline Visit).
- Version 9.3 of SAS® or higher will be the statistical software package used to produce all summaries, listings, statistical analyses, and graphs.
- Updated version of MedDRA will be used for adverse event and pre-treatment coding.
- The current version of the World Health Organization (WHO) drug dictionary will be used for the coding of medications.

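### WHO-DAS total, PCS and MCS are each tested at two-sided 5% with no adjustment, order or success rule; if any one suffices, a false significant result has a chance of about 8-14% in either direction, or about 4-7% in favour of Service Dogs against 2.5% for one test (assumed correlation 0.9 to 0)

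*SAP*

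**What the plan says.** **Primary scores.** Protocol XVIII (Sample Size) lists three primary outcome measures: WHO-DAS 2.0, PCS and MCS. SAP 7.1 counts two primary outcomes covering the same three scores and defines the PCS and MCS outcomes as relative change "adjusted by the baseline scores". Hypothesis 1b is a single quality-of-life claim "as measured by the global mental and physical health component scores of the VR-12", with no statement whether one or both scores must be significant.

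**Error rate.** SAP 7.1 states "The statistical tests for the primary outcome measure will be two-sided at a 5% Type I error rate", for WHO-DAS and again for PCS and MCS. Protocol XVIII (Statistical Methods) states "All statistical tests will be 2-sided and at 5% level of significance". Under SAP 5.4, any p-value at or below alpha "will be considered statistically significant and will be marked with one asterisk".

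**Other descriptions of the primary set.** SAP 2.2.1 says of hypothesis 1a: "The six domain scores and the total WHO-DAS 2.0 score will be utilized for this hypothesis". Protocol III and IV and SAP 2.1 also include the domain scores. Protocol XX (Planned Publications) describes the primary outcomes of the main paper as WHODAS, physical quality of life and PCL. That list omits MCS, the score the trial was sized on, and adds a secondary outcome.

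**Population.** Protocol XVIII defines ITT by randomized assignment, with participants who "will be included in analyses irrespective of their status". It then says analyses of all primary and secondary outcomes "will use both the ITT and PP population", without ranking the two. Protocol III compares participants by the dog they are assigned; SAP 2.1 compares them by the dog they are paired with. SAP 5.3 analyses data as observed, drops data after a dog is replaced from the primary analysis (Protocol XI: in most cases), and makes the missing-data sensitivity analyses depend on missingness being judged substantial.

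**The concern.** Three tests at the full 5% give three chances of a false significant result. Nothing in either document says whether one, two or all three must succeed. The first and second hypotheses in SAP 7.1 are labels, not a testing sequence. Taking the largest of three sample sizes is not a decision rule either, because each was computed at the full 0.05.

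Treating 1a and 1b as separate claims does not remove the gap, since 1b alone has two scores and no rule.

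Protocol I expects the results to inform VA benefits policy on service dogs. As written, one significant score out of three could be presented as the trial's positive result, and a reader could not tell whether a pre-specified bar had been met. A rule chosen after the results are seen cannot restore error control.

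**Working it through.** **1. Inputs** (Protocol XVIII, Table 6 and text). Standardized differences:
- WHO-DAS: 10/13 = 0.769
- PCS: 0.15 × 39.8/10.8 = 0.553
- MCS: 0.15 × 33.2/10.6 = 0.470

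Alpha is 0.05 two-sided for each. The documents give no correlation between the scores, so I assume a common value r from 0 to 0.9, with scores aligned so that a positive sign means benefit.

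**2. The plan's own figures.** n per group = 2(1.960 + 1.036)²/d². For MCS this is 17.96/0.221 = 81.4, so 82. The normal formula gives 31 for WHO-DAS and 59 for PCS; the t-test version gives the stated 32 and 60. Allowing for 25% loss, 82/0.75 = 109.3, so 110 per arm and 220 in total. The sample size reproduces, with alpha not split.

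**3. Familywise error if any one score suffices.** At r = 0, either direction: 1 − 0.95³ = 14.3%. In favour of Service Dogs only: 1 − 0.975³ = 7.3%. For r > 0, integrate over a shared normal factor u with c = 1.96:

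1 − ∫ φ(u) [Φ((c − √r·u)/√(1−r)) − Φ((−c − √r·u)/√(1−r))]³ du

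The one-direction version drops the second Φ term.

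| r | Either direction | Favouring Service Dogs only |
|---|---|---|
| 0 | 14.3% | 7.3% |
| 0.5 | 12.5% | 6.3% |
| 0.7 | 10.9% | 5.5% |
| 0.9 | 8.4% | 4.2% |
| One test | 5% | 2.5% |

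The inflation is about 1.7 to 2.9 times on either count. A PCS-MCS correlation of −0.3 gives 13-14% in either direction, inside the range.

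**4. Hypothesis 1b alone, either score counting.** Either direction: 1 − 0.95² = 9.75% at r = 0, falling to about 7% at r = 0.9. In favour of Service Dogs: 1 − 0.975² = 4.9%, falling to about 3.5%.

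**5. Holm across the three** (smallest p against 0.05/3, next against 0.025, last against 0.05). Simulated error in either direction: 4.9% at r = 0 to 3.0% at r = 0.9.

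**6. Power, two-sample approximation.** These are not the mixed model's power.

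| Quantity | 82 per group | 72 per group |
|---|---|---|
| WHO-DAS alone | 0.998 | 0.996 |
| PCS alone | 0.940 | 0.909 |
| MCS alone | 0.849 | 0.800 |
| All three significant | 0.79-0.85 | 0.71-0.80 |
| MCS under Holm, all effects as designed | 0.83-0.85 | 0.78-0.79 |
| MCS under Holm, only MCS differs | 0.72-0.73 | 0.65-0.67 |

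The all-three row covers a PCS-MCS correlation of −0.3 up to a common 0.9. Its floor at any correlation is the sum of the single powers minus 2: 0.787 at 82 and 0.704 at 72.

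**7. Never-paired participants.** Their number is not given. The protocol aims for 220 paired from about 300 consented, so an upper bound is 300 − 220 = 80, or 80/300 = 27%, reached only if everyone consented were randomized. Assume they are counted with no effect, so that d for MCS becomes 0.470 × (1 − f):
- f = 10%: power 0.77 with 82 per group including them, or 0.81 with 82/0.90 = 91 per group.
- f = 27%: power 0.59 with 82 per group, or 0.73 with 82/0.733 = 112 per group.

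**The case against.** **No passage says that any one score suffices.** This is true. The 8-14% is conditional on that reading, and a reader should not infer that the trial necessarily carries that error. If all three were required there would be no inflation. The documents support neither reading over the other, and that silence is the defect.

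**The two-direction rate overstates the risk of a false case for Service Dogs.** This stands. A reader might infer that such a finding always arises more than 5% of the time. It does not: the rate is 7.3% to 4.2% for three scores, and below 5% throughout for 1b alone. The proper comparator is 2.5%, and both exceed it.

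**Other stronger readings fail.**
- One could count nine primary tests by adding the six domains, but Protocol XVIII and SAP 7.1 both define the primary outcome by the total score. The domains are a wording conflict to reconcile.
- One could say the 0.85 is misstated. It is correct for MCS alone, and no passage claims joint power.
- Running both ITT and PP does not simply double the chances, because the populations overlap.
- The asterisk rule in SAP 5.4 is a display policy that yields to specific sections. It sets no success criterion.

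**Naming ITT is not enough.** This also stands. With data analysed as observed, never-paired participants have no post-pairing scores and drop out of the comparison. The replacement-dog rule conflicts with the ITT definition whichever label is chosen.

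**Holm is one choice among several.** A fixed sequence would also control error. What matters is that one rule is written down in advance.

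**Conclusion.** The concern holds. Three primary scores each receive a full two-sided 5% test and no rule combines them. If any one can carry a positive conclusion, the chance of at least one false significant result is about 14% to 8% in either direction, and about 7.3% to 4.2% in favour of Service Dogs against 2.5% for one test. These figures rest on that condition and on an assumed common correlation of 0 to 0.9. That the rule is missing depends on neither assumption.

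The primary set and the primary population are also described inconsistently, so the pre-specified test cannot be identified from the documents. SAP 5.1 places the final analysis after approval of the SAP. The rule belongs there and must be fixed before outcomes are compared by arm.

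**What to change.** 1. **Primary family.** In SAP 7.1, name WHO-DAS total, PCS and MCS as the primary family and make the six WHO-DAS domains secondary. Reconcile SAP 2.1 and 2.2.1, Protocol III and IV, and the list in Protocol XX (Planned Publications). Keep the baseline adjustment.
2. **Decision rule.** Apply Holm across the three at familywise two-sided 0.05. If the sponsor intends all three to be required, say so and give the joint power (0.79-0.85 at 82 per group, 0.71-0.80 at 72) with its correlation assumption.
3. **Sample size.** In SAP 3.8, add the MCS power under Holm from the working, labelled as a two-sample approximation.
4. **Population.** Name ITT, as Protocol XVIII defines it, as primary and PP as supportive. Reconcile assignment (Protocol III) with pairing (SAP 2.1), and the ITT definition with the exclusion of post-replacement data in SAP 5.3 and Protocol XI. Make the SAP 5.3 missing-data analyses unconditional for randomized but never-paired participants. State that counting them with no effect would lower MCS power below 0.85.

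**Cost.** SAP wording plus a protocol amendment, which the VA Central IRB must approve. No added enrolment is proposed. The real downside is MCS power under Holm: a loss of up to about 2 points if all effects are as designed, and about 12 to 15 points if only MCS differs. Restoring 0.85 for MCS at 0.05/3 would need about 107-109 evaluable per group, or 143-146 per arm after 25% loss. The sponsor should see that figure when accepting the lower power.

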The overall goal of this proposed study is to compare the two treatment groups: Emotional Support Dogs (EMOT) and Service Dogs (SERV) with respect to two specific outcomes – activity limitations and quality of life over 18 months of follow-up. While both treatment groups are expected to show improvement just by virtue of participating in this treatment trial, the committee decided that a 10-point difference in the WHO-DAS 2.0 score would need to be found between treatment groups to be clinically significant. The committee also determined that individual changes of 1 standard deviation (SD) on the PCS and 1 SD on the MCS (Kearney, et al., 2012) would constitute an improvement in both of these measures.

By examining current data, the committee determined that using a 10-point difference between groups in the WHO-DAS 2.0 total score and a change of 15% in PCS and MCS would be conservative estimates of the sample size needed. To calculate sample size, data from two on-going CSP studies were used as an estimate of WHO-DAS 2.0 mean scores and SD. Data from a study used to assess outcomes in participants who participated in a mindfulness-based stress reduction program were used as the PCS and MCS mean and SD (Kearney, 2012).

**TABLE 6: Sample Size Estimates ($\alpha=0.05$) per Treatment Group*
Outcome by Power (1- β)
(Control Group Mean and Standard Deviation)**

		WHO DAS 2.0	MCS	PCS
Power (1-β)				

	EMOT Group Mean (S.D.)	SD=13 & Mean difference between groups	33.2 (10.6)**	39.8 (10.8)**
		Change from EMOT Group Mean:		
		5 point	10%	10%
0.80		108	161	117
0.85		123	185	134
0.90		144	216	156
		7 point	15%	15%
0.80		56	72	53
0.85		63	82	60
0.90		74	96	70
		10 point	20%	20%
0.80		28	41	30
0.85		32	47	35
0.90		37	55	40

* SD from CSP 579

** Kearney et. al, 2012

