### 3.8 Sample Size

The goal for this study is a sample size of 220 including adjustment for subjects who withdraw or are lost-to-follow-up and interim analyses. In order to detect a 15% difference in mean scores for MCS (outcome requiring largest sample) over the 18-months of follow-up, at a statistical significance level of 0.05 (two-tailed test) and a power of 0.85, 82 participants per group will be needed, and 110 participants per treatment (220 total) will be required to account for a maximum of 25% post-pairing participant loss or dropout rate (see protocol). This sample size results in an expectation of 110 subjects in each of the treatment groups. For challenges in the recruitment of participants or in the pairing (or availability) of dogs, sample size will be revisited and adjusted accordingly taking into account the study's post-pairing termination rate. For 80%, a sample size of 72 per group is needed, and 90 participants per treatment (180 total) to account for a 20% post-pairing termination rate or 85 (170) to account for a 15% termination rate. When such challenges occur, a sample size of 180 will be the aim.

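### The additional random-intercept analysis in SAP 7.1 understates the standard error of the group-by-time slope difference if time is linear and Veterans' slopes vary

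*SAP*

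**What the plan says.** SAP 7.1 first sets out the primary analysis, a generalized linear mixed model for WHODAS 2.0 and separate ones for PCS and MCS. On error control it states: "The statistical tests for the primary outcome measure will be two-sided at a 5% Type I error rate". Its closing paragraph adds a further analysis for all the hypotheses of that section: linear mixed models with random intercepts. Only the WHODAS version is written out. The scores are to be "regressed on time and the group x time interaction with random intercepts added for participants", and the intercepts are said to take care of the within-person correlation. The paragraph motivates random coefficients by saying that each subject then has an own regression equation, "making it possible to evaluate whether subjects differ in their means and/or response patterns over time".

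Protocol XVIII (Primary Outcome Measures) has the same WHODAS model and adds a random-intercept model for PCS and MCS. For this analysis neither document gives a random slope, a residual covariance structure, robust standard errors or the coding of time. The shell in SAP Table 13 lists SP(EXP), but it is headed as output of the primary GLMM.

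**The concern.** A random intercept lets Veterans differ in level only; all slopes within an arm are taken as equal. If true slopes vary, part of that variation is absorbed into the residual and the rest is lost, so the standard error of the between-arm slope difference comes out too small.

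Differing slopes are plausible here. Both documents provide for dogs being removed or replaced during follow-up, and the SAP's own rationale anticipates individual patterns. At stake is a supporting analysis of all three primary measures that could seem to confirm, or compete with, the primary result on the strength of p-values that reject too often.

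**Working it through.** **Plan's own figure.** SAP 3.8: "In order to detect a 15% difference in mean scores for MCS" with "a power of 0.85, 82 participants per group will be needed". Protocol Table 6 gives an MCS mean of 33.2 and SD of 10.6, so the difference is 0.15 × 33.2 = 4.98. Then n = 2 × (10.6/4.98)² × (1.960 + 1.036)² = 81.4, rounded up to 82. For "a maximum of 25% participant loss or dropout rate", 82/0.75 = 109.3, rounded up to 110, so "110 participants per treatment (220 total) will be required". The figures reproduce. They come from a two-sample comparison of means and do not depend on the additional model.

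**Inputs for the check.** Protocol Table 6 gives the WHODAS SD ("SD=13 & Mean difference between groups"). Visits are months 3 to 18 every three months, with or without baseline. Assumed, because the documents give neither: intraclass correlation 0.65, and slope SD τ of 0, 3, 6 or 9 points per 18 months, independent of the intercept. Complete data are also assumed. Residual variance is s² = 0.35 × 13² = 59.15.

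**Closed form, linear time, group main effect included.** Let time run in units of 18 months, with m visits and Sxx the sum of squared deviations of visit times.
- True variance of one subject's fitted slope: s²/Sxx + τ².
- The random-intercept fit estimates the residual variance as s² + τ²·Sxx/(m−1), so it uses s²/Sxx + τ²/(m−1).

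Only 1/(m−1) of the slope variance is counted. The standard-error ratio R is the square root of model over true variance, and type I error is 2 × [1 − Φ(1.96 R)]. The number per arm cancels from R.

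Months 3–18: m = 6, Sxx = 17.5/36 = 0.486, s²/Sxx = 121.68.
- τ = 3: 123.48/130.68, R = 0.97, error 5.7%
- τ = 6: 128.88/157.68, R = 0.90, error 7.6%
- τ = 9: 137.88/202.68, R = 0.82, error 10.6%

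Baseline added: m = 7, Sxx = 28/36 = 0.778, s²/Sxx = 76.05.
- τ = 3: 77.55/85.05, R = 0.95, error 6.1%
- τ = 6: 82.05/112.05, R = 0.86, error 9.3%
- τ = 9: 89.55/157.05, R = 0.76, error 13.9%

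At τ = 0, R = 1 and the error is 5.0%.

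**Model as written (time and group × time, no group main effect).** The compound-symmetry covariance was fitted to the true one by large-sample maximum likelihood, and the model-based standard error was compared with the sandwich one.

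| Slope SD | Months 3–18: R, error | Baseline added: R, error |
|---|---|---|
| 3 | 0.96, 5.9% | 0.95, 6.4% |
| 6 | 0.87, 8.7% | 0.83, 10.2% |
| 9 | 0.78, 12.6% | 0.73, 15.5% |

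A simulation of 4,000 null trials per setting gave 6.4, 8.2 and 12.9%, and 6.1, 10.5 and 15.7%. It gave 5.8% at slope SD 0, a little above nominal, so the large-sample figures are preferred at the low end.

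**Categorical time.** The omnibus group × time test has error 5.0–5.7% over the same slope SDs. Single late contrasts are still affected. For month 18 against baseline at τ = 9, the model variance is 2 × (59.15 + 81 × 0.778/6) = 139.3 and the true variance is 2 × 59.15 + 81 = 199.3, so R = 0.84. With SD 10.6, intraclass correlation 0.6 and slope SD 10, it falls to 0.78.

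**The case against.** **Time coding.** The result needs linear time, and the plan says only that scores are regressed on time. Table 13 sets months out as columns with Type III tests, so categorical time is open. This stands. A reader might infer that the analysis is invalid whenever trajectories differ; the documents do not support that, because the categorical omnibus test is nearly unaffected.

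**Covariance.** The wording might mean a repeated-measures residual covariance with intercepts added. An exponential structure plus a random intercept would bring the error to 5.1–6.4% with a group main effect, or 5.5–8.8% without. But the text gives the intercepts the job of handling the correlation, and SP(EXP) appears only in the primary model's shell. The pure random-intercept reading is the better one.

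**Size.** No slope variance is given. At slope SD 3 the excess is about one percentage point. Slope SD 9 implies a month-18 SD of √(169 + 81) = 15.8, against the planned 13. This stands, so the size is conditional.

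**Scope.** A reader might take all hypotheses to mean every hypothesis in the trial, or think the primary test is affected. The sentence sits in SAP 7.1 and covers WHODAS, PCS and MCS. Secondary outcomes have their own models, the economic regressions correct their standard errors for repeated observations, and the primary GLMM is separate.

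**Group main effect.** Its absence is not an error in itself. With baseline among the responses, equal starting means are an accepted constraint under randomization. The plan does not say whether baseline is a response.

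**Stated purpose.** The sentence on random coefficients is generic, and a random intercept does address differing means. It cannot address differing patterns over time, so that mismatch remains.

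**Conclusion.** The point holds for the additional analysis, conditionally. With linear time and any non-zero slope variance, the random-intercept model understates the standard error of the slope difference. For the model as written, type I error is about 6%, 9–10% and 13–16% at assumed slope SDs of 3, 6 and 9 points per 18 months (SD 13, assumed intraclass correlation 0.65). Adding only the group main effect leaves most of the excess, so the random slope is the main repair. The direction follows from algebra; the size rests on assumptions the documents cannot settle. This is worth correcting before analysis, but it does not threaten the primary result or the sample size.

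**What to change.** In SAP 7.1 and Protocol XVIII, for the additional analysis of WHODAS, PCS and MCS:

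- State that time is linear, and add a random slope with unstructured intercept–slope covariance and small-sample degrees of freedom. An unstructured residual covariance or robust standard errors would also serve.
- Say whether baseline is in the response vector. If it is not, include the group main effect.
- Name a fallback covariance in case the random-slope model does not converge. If the fallback has no random slope, delete the claim about subject-specific patterns.

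The cost is about one line of model code and a few sentences of text. Confidence intervals will be slightly wider, and convergence may sometimes fail. Sample size and the primary GLMM do not change.
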